6. MILESTONES

Milestone	Planned Date
Start of study/data collection	17 July 2017
End of data collection	31 July 2018 (The time-point when approximately 1000 dabigatran treated patients with completed observation time are expected to be registered in the database and data extraction will be done for the analysis)
Registration in the EU PAS register	13 July 2017 (registration no. EUPAS 17165)
Final report of study results:	31 December 2018 (Considering that the observation time for 1000 dabigatran treated patients is completed by 31 July 2018.)

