9. RESEARCH METHODS**9.1 STUDY DESIGN**

This is an observational, multinational, multicentre, study in patients with NVAF presenting to a hospital with a first acute ischemic stroke. The study is based on existing data recorded in the SITS International Registry by physicians in European countries, such as Italy, United Kingdom, Czech Republic, Sweden, Germany, Poland, Spain, Finland, Portugal, Slovakia, Denmark, Estonia, Norway Belgium, Hungary, Slovenia, Croatia, Austria, Lithuania, France, Greece, Netherlands, Ireland, Ukraine and Iceland. All patients with NVAF will be included that present with the first ever ischemic stroke. For these patients baseline and demographics variables are available such as medical history including comorbidities and concomitant medications. Characteristics will further be used to estimate common stroke (CHADS₂, CHA₂DS₂-VAS_c) and bleeding (HAS-BLED) risk scores. Details on NVAF and secondary stroke prevention: time since first diagnosis, prior anticoagulation treatment, dose, and stroke severity of index event measured by National Institute of Health Stroke Scale (NIHSS) score, are recorded in the registry.

For patients that receive dabigatran within 3 months of the index event, details on post-stroke treatment (time from hospital admission – start and dose of dabigatran treatment for stroke prevention in NVAF, concomitant medication) will be analysed. Variables for physician's decision when to initiate oral anticoagulation with dabigatran post-ischemic stroke and the dose selected will be analysed.

In addition any start/stop of dabigatran treatment and doses prescribed will also be assessed at discharge and at 3 months after the index event.

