At baseline: Demographic data, NIHSS and pre-stroke mRS, blood pressure, laboratory values (plasma glucose, cholesterol, coagulation status, liver function, kidney function,) medical history including comorbidities and concomitant medication, results of imaging scans, CHADS₂, CHA₂DS₂-VASc and bleeding risk by HAS-BLED scores.

At 24 hours: NIHSS score, blood pressure, laboratory and imaging scans if performed.

During hospital stay: details of concomitant medications, additional imaging scans prior to start of dabigatran treatment, any start/stop/change dabigatran treatment any results of the imaging scans

At 7 day or discharge if occurred earlier than 7 days: Date/time discharge, NIHSS scores, blood pressure, type of stroke and AF, medications

SITS is an academic-driven, non-profit, international collaboration. It is an initiative by the medical profession aimed at driving excellence in acute and secondary stroke treatment, and to develop new knowledge and leading research.

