9.9 LIMITATIONS OF THE RESEARCH METHODS**Non-interventional study based on existing data**

The quality of a study based on existing data relies on accuracy of recorded data. Important data may not be available. In the absence of randomisation and blinding, it can be difficult to control for bias and confounders.

Selection bias

There is a risk of selection bias at the patient level. Sites might preferentially include "interesting" cases to the SITS study. To minimize selection bias at the patient level, centres were reminded by e-mail every 3 months that all consecutive patients from each site who meet entry criteria must be included in the SITS-Registry.

Lost to follow up

As with all observational studies a loss to follow up can occur. In this study this will affect the patients with a pre-planned follow up (patients initiating dabigatran within the 3 months after the index event). However, considering the short time period of the follow up and the lost to follow up at 3 months in the general SITS Registry being 20%, a similar percentage of lost to follow up is expected in this study as well.

Channeling bias

Protocol for observational studies based on existing data**BI Study Number 1160-0235****c03412460-01**

Proprietary confidential information © 2017 Boehringer Ingelheim International GmbH or one or more of its affiliated companies

Channeling bias can occur due to preferential prescribing in relation to different risks for the events of interest: e.g., if dabigatran would be more often prescribed to higher risk patients compared to other treatments,

In order to assess potential channeling bias patients not receiving dabigatran within 3 months of the index event will be assessed. For example, patients initiating VKAs, other NOACs or no oral anticoagulation therapy will be assessed according to important patient baseline characteristics (e.g. age, sex, comorbidities, stroke and bleeding risk scores, concomitant medications).

Confounding

As in any observational study, confounding may affect the estimation of association between variables and clinical outcome events of interest and statistical techniques such as adjustment for covariates, stratified analyses, matching, etc. can be used to correct for these. But as only major confounders for selected research questions can be captured, unmeasured confounding may remain.

Exploratory analyses

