- Patient's Bleeding risk factors
- Coagulation Lab parameters
 - APTT
 - ECT Time
 - Thrombin Time

- INR
- Patient medical history (e.g. previous GI bleed, etc)
- Patient co-morbidities (e.g. heart failure, diabetes, etc)
- Patient renal function
- History of previous stroke, transient ischemic attack, or systemic embolism
- Co-medication affecting haemorrhagic risk (e.g. ASA, clopidogrel, NSAIDs, verapamil)
- Co-medication other (e.g. antihypertensive, etc.)
- Recommendation from specialist (e.g. Cardiologists)
- Other
 - Specify other (Reasons for the dose of oral anticoagulation)

3.5 Covariates:

The following variables will be considered to characterize the patients in addition to the key variables defined for secondary outcomes B

- Patient demographics (, e.g. weight, smoking)
- Country
- Stroke severity based on National Institute of Health Stroke Scale (NIHSS),
- pre-stroke functional status by mRS
- Signs of current/ acute infarction in the brain imaging scans
- Prior TIA

- Time since AF diagnosis
- Antithrombotic treatment for stroke prevention history prior index event
- Comorbidities (Hypertension, Diabetes, Hyperlipidaemia, Congestive Heart Failure, Systemic embolism, MI, PAD, complex aortic plaque, abnormal kidney function, abnormal liver function,
- Prior Bleeding (history and/or predisposition to bleeding) Relevant comedications at time of index stroke (as listed in Appendix 7.1)
- CHADS2
- Type of Acute Intervention (Intravenous thrombolysis, Intraarterial thrombolysis, Mechanical thrombectomy)
- Time from hospital admission – start and dose of dabigatran treatment for stroke prevention in NVAF (
- ...

4 Study design

Data from the SITS-International AF registry will be extracted for the purpose of analysis. Patients with NVAF presenting with their first ever acute ischemic stroke who are registered in the SITS International Registry from 1 July 2014 until approximately 31 July 2018 and meeting the inclusion and not having the exclusion criteria will be included in the study.

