6.1 Primary Analysis

This analysis will be done for NVAF patients presenting with first ischemic acute stroke and treated with dabigatran within 3 months of index event.

To describe the distribution of dabigatran treatment initiation times in patients with non-valvular atrial fibrillation (NVAF) after hospitalization for first-ever ischemic stroke (the index event) treated with dabigatran, we will

1. Create a histogram of initiation times by day.
2. Calculate mean, standard deviation and 95% (Standard Normal) confidence intervals (CI) of the Mean, as well as the median, interquartile ranges, minimum and maximum values.
3. Create frequency table by time periods. Give the absolute count of subjects and the proportion of subjects in each group. The time periods to be considered are 0-24h, >24-72h, >3-7d >7-14d, >14-28d, >28d-3m, however these categories may be revised depending on the distribution of initiation times to ensure sufficient patient numbers in each category.

We do not expect to have any missing values in the time to dabigatran treatment initiation. However, if there are missing values collected, they will be summarized in the frequency table as a separate category. Proportions for all other categories will not include the missing values in the denominator (as this is what has been done in previous works for all previous SITS-MOST and/or SITS-ISTR publications [P07-00880, P08-11746].). The proportion of missing values will be out of all subjects sampled.

6.2 Secondary Analysis:

These analyses will be done for NVAF patients presenting with first ischemic acute stroke and treated with dabigatran within 3 months of index event.

6.2.1 To describe baseline characteristics for patients treated with dabigatran according to time of dabigatran initiation.

Descriptions will only be done for the subgroups (of time to initiation) consisting of at least 100 patients. We Will:

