▪ Warfarin derivatives
▪ New OAC (NOAC)
• If NOAC
○ Dabigatran
○ Apixaban
○ Rivaroxaban
2h follow up
Systolic Blood Pressure
Diastolic Blood Pressure
NIHSS
24h follow up
NIHSS
Systolic Blood Pressure
Diastolic Blood Pressure
Current Infarct CT/MR
ASPECTS Score CT/MR
Local Haemorrhage CT/MR
Remote Haemorrhage CT/MR
Cerebral Oedema CT/MR
At discharge/ 7d
Diagnosis of NVAf at (previous, at or during hospital stay)
Oral anticoagulation (OAC) at = YES
▪ Warfarin derivatives
▪ New OAC (NOAC)
• If NOAC
○ Dabigatran
○ Apixaban
○ Rivaroxaban
Date & time of OAC start: DD/MM/YYYY, time: clock
OAC at discharge = No
1) Date of foreseen start of OAC if not started during hospital stay
Date: DD/MM/YYYY
Aspirin
mRS Score
NIHSS
Systolic Blood Pressure
Diastolic Blood Pressure
Date of
Dipyridamole
Clopidogrel
Other Antiplatelet

Anticoagulants Oral
Dabigatran
Dabigatran Dose
Date of Dabigatran Initiation
Anti Diabetic Oral
Antihypertensive Oral
Statin
Other
Type Of Stroke
Type Of Stroke Ischemic
Type Of Stroke Haemorrhagic
Date Time Of Death
Cause Of Death
At 3-months
Modified Rankin Scale score
If mRS=6=Dead, date/time of death
Cause of death
Patients with NVAf at discharge/ 7d but patient has not been prescribed Warfarin or NOAC (Dabigatran, Apixaban, Rivaroxaban at
1) Has the patient been prescribed Dabigatran after discharge?
If YES questions below will also be shown.
2) Date of initiation of Dabigatran for stroke prevention in NVAf
Date: DD/MM/YYYY
Dose:
Patients with NVAf has been prescribed dabigatran at discharge
Is the patient continuing the prescribed Dabigatran at 3 months follow up since start of the treatment?
- Yes/ No/ Unknown
If No, date of stop of treatment:
Reason for stop of treatment:
- Has the OAC treatment been changed?
If Yes,
Which treatment:

7.2 Appendix 2

CHADS₂ Stroke Risk Score

CHADS ₂ components	Points
Congestive heart failure	1
Hypertension	1
Age 75 years or older	1
Diabetes mellitus	1
Prior cerebral ischemia (i.e., stroke, TIA)	2
Maximum score	6

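### Unless a 3-month form is required, the primary distribution of dabigatran start times is tilted towards early starts, because starts after discharge are identified only at 3 months

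*SAP*

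**What the plan says.** SAP 6.1 sets the primary population: "This analysis will be done for NVAF patients presenting with first ischemic acute stroke and treated with dabigatran within 3 months of index event". It plans a daily histogram, the mean and median with spread, and a table of six time periods. On missing data it says "We do not expect to have any missing values in the time to dabigatran treatment initiation"; any that occur get a separate row and leave the other denominators.

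Starts are captured at several points. Protocol 9.4 records, during the hospital stay, "any start/stop/change dabigatran treatment". Protocol 9.1 adds that "any start/stop of dabigatran treatment and doses prescribed will also be assessed at discharge and at 3 months after the index event". SAP Appendix 7.1 dates in-hospital starts on the discharge/7-day form. For patients with NVAF not prescribed warfarin or a NOAC by then, the 3-month block asks "Has the patient been prescribed Dabigatran after discharge", followed by date and dose. The discharge form otherwise holds only a foreseen start date for any oral anticoagulant.

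Protocol 9.9 puts loss at 3 months in the general registry at 20%, says that loss will affect patients initiating dabigatran, and states that "a similar percentage of lost to follow up is expected in this study as well".

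The nearest thing to a follow-up requirement is in Protocol 6, where "approximately 1000 dabigatran treated patients with completed observation time are expected to be registered in the database". The eligibility criteria (Protocol 9.2, SAP 4.1 and 4.2) do not mention a 3-month form. Neither does SAP 4, which takes patients "registered in the SITS International Registry from 1 July 2014 until approximately 31 July 2018 and meeting the inclusion" and not the exclusion criteria.

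**The concern.** Entry to the primary set can depend on the quantity being described. A patient who starts in hospital is known to be a starter whether or not the 3-month contact succeeds. A patient who starts after discharge is known to be one only if it succeeds. If no form is required, loss at 3 months removes late starters and leaves early ones.

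Time to initiation is the only primary outcome, and a larger sample does not reduce a tilt of this kind. The report would also look complete: the missing-value row can hold only patients already known to be treated, so a late starter who was never identified appears nowhere.

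**Working it through.** The documents derive no figure here, so there is nothing to reproduce. The 20% is a quoted expectation.

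**Inputs.** Loss L = 20% (Protocol 9.9), with 10% and 30% as alternatives. n = 1000 observed starters (Protocol 9.5). The documents do not give the true post-discharge share s or the loss within that group, so s is varied and L is applied to that group by assumption. In-hospital capture is taken as complete, no 3-month form is required, and loss is unrelated to start time among post-discharge starters.

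**Formula.** Share seen: s' = s(1−L) / [(1−s) + s(1−L)]. The odds of a recorded post-discharge start are multiplied by 1−L, i.e. by 0.8. Half-width = 1.96 √[q(1−q)/1000], where q is the share seen in the category concerned. With an even spread over k late periods, the true share s/k per period is seen as s'/k.

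Example, s = 30%: s' = 0.24/(0.70 + 0.24) = 25.5%, a shift of 4.5 points against a half-width of 2.7. Over three periods, 10.0% each is seen as 8.5%, a shift of 1.5 against 1.7.

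At L = 20% (shift / half-width, in points):

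| True s | Pooled share seen | All in one period | Two periods, each | Three periods, each |
|---|---|---|---|---|
| 5% | 4.0% | 1.0 / 1.2 | 0.5 / 0.9 | 0.3 / 0.7 |
| 10% | 8.2% | 1.8 / 1.7 | 0.9 / 1.2 | 0.6 / 1.0 |
| 20% | 16.7% | 3.3 / 2.3 | 1.7 / 1.7 | 1.1 / 1.4 |
| 30% | 25.5% | 4.5 / 2.7 | 2.2 / 2.1 | 1.5 / 1.7 |
| 50% | 44.4% | 5.6 / 3.1 | 2.8 / 2.6 | 1.9 / 2.2 |

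**Other loss rates.** At 10% loss the pooled shift is 0.5/0.9/1.6/2.2/2.6 points at the same shares, always below the half-width (1.3/1.8/2.4/2.8/3.1). At 30% loss the pooled shift is 1.5/2.8/5.1/6.9/8.8 points. Even over three periods it then exceeds the half-width at a 20% share (5.11/3 = 1.70 against 1.35).

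**Continuous summaries.** These use illustrative inputs that are not in the documents: in-hospital mean 5 days (SD 4), post-discharge mean 30 days (SD 20). The fall in the mean is 25 × the pooled shift: 0.5/0.8/1.1/1.4 days at s = 10/20/30/50%, against CI half-widths of 0.6/0.8/0.9/1.1. With lognormal shapes the median goes from 4.31 to 4.22, 4.88 to 4.66, 5.77 to 5.32 and 10.57 to 8.58 days.

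**Restricting to completed forms.** With equal 20% loss in both groups, the shares seen equal the true shares. The set keeps 1000 × [0.8(1−s') + s'] = 808/816/833/851/889 patients at s = 5/10/20/30/50%. With 10% loss among in-hospital and 20% among post-discharge starters, the residual shift in the pooled share is 0.9(1−s)/[0.9(1−s) + 0.8s] − (1−s) = 1.8/2.4/2.9 points at s = 20/30/50%, instead of 3.3/4.5/5.6.

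**The case against.** **The milestone wording may already settle it.** If it means that a 3-month form was obtained, both kinds of starter are lost alike and the differential bias largely disappears. But it is a planning date, not an analysis-set rule, and it can equally mean that three months have elapsed. Protocol 9.9, which expects loss among dabigatran initiators, fits the elapsed-time reading better. The point therefore stays conditional.

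**The limitation is already disclosed.** Protocol 9.9 admits loss to follow-up. SAP 5 says that the sample is conditional on starting before death, a second stroke or leaving care, and that findings are hypothesis generating. That covers patients who did not start. It does not cover starts that happened and went unrecorded, nor unequal loss of early and late starts.

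**The size may be small.** This stands in large part. Taking the pooled figures, a reader might infer that the primary result is off by more than sampling error once about 8% of starts occur after discharge. The plan does not support that. SAP 6.1 does not tabulate a pooled post-discharge share, and the 8% threshold carries over to its table only if all such starts fall in one period. Nor do the documents say that loss among post-discharge starters is 20%; that is a registry-wide rate carried over. Protocol 9.8 describes contacting centres about missing data, which could lower it.

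**Capture may be wider than listed.** This also stands. Appendix 7.1 is a list of particularly important variables and may be incomplete. The foreseen date on the discharge form can flag probable late starters, although it is a plan for any oral anticoagulant, not a recorded dabigatran start.

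**Conclusion.** The concern holds in conditional form. Unless a 3-month form is required, the primary distribution is tilted towards early starts, and nothing in SAP 6.1 would reveal it. The direction is clear; the size is not known.

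At 20% loss the effect on the planned six-period table is modest: within sampling error when post-discharge starts spread evenly over three periods, and beyond it only when they concentrate in one (shares of about 8% or more) or two (about 30%). The median moves little unless the post-discharge share is near half. All of this rests on full in-hospital capture, on the variable list being complete for post-discharge starts, and on the registry's 20% applying to that group.

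The documents do not support a stronger conclusion that the primary result is materially wrong. They do support making the gap visible, since the data are already held.

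**What to change.** In SAP 6.1:

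(a) Report the number of eligible patients with NVAF and no oral anticoagulant at discharge who have no 3-month form, and how many of them had a foreseen anticoagulant start date. This shows how many late starts could have been missed.

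(b) Beside the all-starters table, give the same summaries restricted to starters with a completed 3-month form. State that this removes the bias only if form completion is unrelated to start time. If the milestone wording does mean an obtained form, the two tables coincide and one sentence saying so is enough.

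Protocol 9.7 already allows sensitivity analyses to be added in the SAP; none on this point appears in the SAP text available.

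The cost is wording, one count with a breakdown and one extra table. At 20% loss in both groups and shares of 5 to 50%, the restricted table holds about 810 to 890 of 1000 patients, so the largest half-width rises from 3.1 to 3.4 points (1.96 √(0.25/808)). If loss differs between the groups some bias remains: about 1.8 to 2.9 points in the pooled share with 10% against 20% loss, at shares of 20 to 50%. The restricted table should therefore accompany the all-starters table, not replace it.

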9.4 DATA SOURCES

SITS – International Stroke Treatment Registry (ISTR)

Data from the SITS-International AF registry will be extracted for the purpose of analysis. The SITS-International registry is an ongoing, prospective, internet-based, academic-driven, multinational, stroke register. All centres registering patients in the SITS registry are required to accept the basic rules of participating in registry: consecutive registration of all patients with stroke symptoms receiving alteplase (if the centre registers only patients treated with intravenous thrombolysis), irrespective of whether treatment was on- or off-label. If the centre registers all stroke patients in the registry, consecutive registration of all patients with

Protocol for observational studies based on existing data**BI Study Number 1160-0235****c03412460-01**

Proprietary confidential information © 2017 Boehringer Ingelheim International GmbH or one or more of its affiliated companies

stroke symptoms is obligatory. Death is collected separately in the SITS registry; however it is linked to the other outcomes at the 3 month time point from the index event. Register data has some inherent limitations. One of the most important limitations is we do not have any regular monitoring for source data verification, although monitoring was done during the period when the Safe Implementation of Thrombolysis in Stroke-Monitoring Study (SITS-MOST) was done [P07-00880]. In 2011-12, Karolinska Trial Alliance performed an independent monitoring of some selected Swedish centres and verified that data entered in the registry from these centres are accurate. Moreover, it is important to note that all results published based on SITS data with regard to baseline and demographic characteristics and outcome are comparable to other published data from randomised trials, registry data and centre data. SITS registry has a logical automatic validation system, which prevents the entry of erroneous or impossible data in the registry, to some extent. Regular checking of online report and prompt action by contacting centre is also a part of the work for SITS International Coordination members. Moreover, data are downloaded and cleaned regularly for scientific publications.

The SITS registry has implemented extended data entry for AF and oral anticoagulation since June 2014.

Specification of data collection from the index stroke event

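### SAP 6.1 bases each start-period share on dated starters only, which is unbiased only if missing dates are unrelated to timing; splitting undated starters by recording form would bound the shares.

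*SAP*

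**What the plan says.** The primary outcome is time from the index event to dabigatran start, summarised as a distribution and in the periods "0-24h, >24-72h, >3-7d >7-14d, >14-28d, >28d-3m", which may be revised (SAP 6.1). On missing start times, SAP 6.1 says "We do not expect to have any missing values in the time to dabigatran treatment initiation". If there are some, "they will be summarized in the frequency table as a separate category", and "The proportion of missing values will be out of all subjects sampled". For the other rows, "Proportions for all other categories will not include the missing values in the denominator". The reason given is earlier practice in the registry's publications. Protocol 9.7 states that convention for baseline characteristics; the SAP carries it over to the primary outcome. The histogram, mean and median in SAP 6.1 have no stated rule for undated starters.

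SAP Appendix 7.1 lists start information at two points:

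- **Discharge/7d form** (day 7, or discharge if earlier, per Protocol 9.4): whether oral anticoagulation (OAC) has been given, which drug, and the date and clock time of start. Where the answer at discharge is No, there is a field "Date of foreseen start of OAC if not started during hospital stay".
- **3-month form:** patients not on an oral anticoagulant at the earlier form are asked whether dabigatran was prescribed since, with a separate field for the start date. A second block, "Patients with NVAf has been prescribed dabigatran at discharge", asks about continuation, stopping and change.

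**The concern.** A starter with no date is not wholly uninformative. A start recorded as having happened on the discharge/7d form lies between the index event and that form. A patient not started at that form, and first reported at 3 months, began between the two contacts. SAP 6.1 treats both as if nothing were known and computes shares among dated starters.

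Missingness could plausibly be related to timing. Starts in hospital are entered close to the event, whereas later ones are dated in retrospect at 3 months. On the listed wording, a patient prescribed dabigatran at discharge but starting later might reach only the continuation block, which lists no start date. At stake is the study's primary result: how long physicians wait. The planned confidence intervals would not reflect a shift of this kind.

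**Working it through.** **Plan's own figure.** There is none to reproduce. The documents state no missing-date rate, and Protocol 9.5 bases the size of about 1000 on availability.

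**Inputs.** From the documents: N about 1000 (Protocol 9.5) and the denominator rule (SAP 6.1). Assumed: the true share p starting by the discharge/7d form, and the missing-date rates mE for those starts and mL for later ones.

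**Formula.** The SAP share is

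p(1−mE) / D, with D = p(1−mE) + (1−p)(1−mL).

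Subtracting p gives the bias p(1−p)(mL−mE) / D. It is positive when mL > mE, zero when they are equal, and negative when mE > mL.

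**Later dates missing more often, mE = 1%.**

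| True p | mL | Calculation | SAP share | Shift (points) | Missing overall |
|---|---|---|---|---|---|
| 65% | 5% | 0.6435/0.9760 | 65.9% | +0.9 | 2.4% |
| 65% | 10% | 0.6435/0.9585 | 67.1% | +2.1 | 4.15% |
| 65% | 20% | 0.6435/0.9235 | 69.7% | +4.7 | 7.65% |
| 50% | 5% | 0.495/0.970 | 51.0% | +1.0 | 3.0% |
| 50% | 10% | 0.495/0.945 | 52.4% | +2.4 | 5.5% |
| 50% | 20% | 0.495/0.895 | 55.3% | +5.3 | 10.5% |

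With mE = 0 and p = 50%, mL of 5%, 10% and 20% gives 51.3%, 52.6% and 55.6%.

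**Other directions, p = 50%.** Equal rates of 5% give 50.0%, so no bias. With mE = 10% and mL = 2%, the share is 0.45/0.94 = 47.9%, a shift of −2.1 points.

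**Sampling error for scale.** 1.96 × √(0.65 × 0.35/1000) = 3.0 points; at p = 50% it is 3.1 points. Only the 20% rows exceed this.

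**What the forms add.** Take N = 1000, p = 50%, mE = 0 and mL = 10%, so 0.10 × 500 = 50 starters are undated. Ignoring the form, the early share is bounded by 500/1000 = 50.0% and 550/1000 = 55.0%. If all 50 are known to have started after the form, the share is exactly 50.0%. If 30 are known and the status of 20 is unclear (again an assumption), the bounds are 500/1000 = 50.0% and 520/1000 = 52.0%. The gain therefore depends on how many can be placed. Adding undated starters to every denominator without placing them is not a repair: with 5% missing in both groups it gives 0.475 where the truth is 0.50.

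**The case against.** The strongest reply has four parts.

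- **Direction is not shown.** Nothing in the documents says that later starts lack dates more often. The two earliest periods need clock time, which is requested on the discharge/7d form, so unclassifiable times could concentrate among early starts. This stands. A reader might infer that the early shares are overstated; the documents support only the conditional statement.
- **Dates may well be complete.** Protocol 9.4 admits that "we do not have any regular monitoring for source data verification", but that concerns accuracy more than blank fields. Protocol 9.8 describes automatic prompts for blanks, completeness checks every six months and requests to sites to fill gaps. These do not guarantee that none are missing, and the SAP writes a rule for the case. Even so, it would be too strong to call its expectation baseless. Nor can a gap in the forms be inferred from Appendix 7.1, which is a selection of variables. The foreseen-date field belongs to patients with no OAC at discharge, and the 3-month block for patients not yet on an anticoagulant does ask for an actual date.
- **The undated patients are visible.** SAP 6.1 gives them their own row, out of all subjects, so a reader can compute shares over all starters and crude bounds. This stands, but a reader cannot split that row by form.
- **The forms do not always place the start.** It is tempting to read dabigatran on the discharge/7d form as a start by that date. That fails for a patient prescribed it there for later use, who would be misfiled as early. Only a recorded start supports the bound. Even then, an undated early start can span three periods and a later one most of the six, so period bounds may stay wide.

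**Conclusion.** The point holds as a conditional one about the contingency rule for the primary outcome. The rule is unbiased only if missing dates are unrelated to timing. The SAP gives no argument for that and no sensitivity analysis, and it leaves usable information on the forms unused. The shift is about 1 to 5 points for 5% to 20% missing late dates with few or no early ones missing. It reverses if early dates are missing more often and is zero if none are missing. These sizes rest on assumed missing rates and an assumed early share. Only the 20% scenario exceeds sampling error at 1000 patients, and no document gives such a missing-date rate. The documents do not support a claim that the planned shares are biased, that the bias runs towards early starts, or that the plan conceals the undated patients. The improvement is worth making because it costs little.

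**What to change.** Keep the table in SAP 6.1 as planned. Add that, if any start date is missing, the missing row is split into:

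- (a) undated, recorded as already started (OAC = Yes) on the discharge/7d form;
- (b) undated, not started at that form and first reported at 3 months;
- (c) undated, with start status at that form unclear, for example prescribed at discharge or with only a foreseen date.

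As a sensitivity analysis, report lower and upper bounds for each period share and for the median, with all starters in the denominator. Place (a) between the index event and the form, (b) between the form and 3 months, and (c) anywhere from the index event to 3 months. Use a foreseen date only in a sensitivity analysis, never as the actual start.

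The cost is a short addition to the SAP, slightly more programming on fields already listed, and wider stated ranges if dates turn out to be missing. The main table still matches the earlier registry convention.

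This does not reach late starters who are never identified because the 3-month form is absent. Protocol 9.9 expects about 20% loss to follow-up at that point; those patients never enter the missing row and need separate treatment.
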